Our team is comprised of highly experienced adolescent HIV prevention researchers, including [name] and [name], who have a long history of research that seeks to address the key health issues facing South African adolescent girls while at the same time protecting this vulnerable population. The research sites have considerable experience in conducting clinical research in adolescent populations.

Figure 2. HIV incidence (%) by age and sex in South Africa

[figure not shown]
[figure not shown]

Figure 3. Adolescent pregnancy in South Africa, 2010-2013

Our study, PrEP-PP (PrEP in Pregnant and Postpartum women) will determine the distribution of women across the PrEP cascade (i.e. PrEP initiation, retention, and adherence) in a cohort of HIV- pregnant and breastfeeding adolescent girls and women in two public health facilities in South Africa to inform policymakers about the efficacy of PrEP integration into antenatal (ANC) and postnatal care in high HIV incidence communities.

2. Study objectives:

The objectives of the study are to:

1. Determine the distribution of women across the PrEP cascade:
 - (1) Evaluate the proportion of pregnant and breastfeeding women who initiate PrEP out of all women offered PrEP
 - (2) Evaluate the proportion of pregnant and breastfeeding women who are retained in the PrEP cohort
 - (3) Evaluate the proportion of pregnant and breastfeeding women who initiate PrEP who adhere to PrEP using objective dried blood spot measures and subjective measures of self-reported pill count and adherence
 - (4) Evaluate the proportion of pregnant and breastfeeding women on PrEP (and not on PrEP) who acquire HIV, who transmit HIV to their infant, and who report adverse events
2. Evaluate patient and provider-level factors associated with the PrEP cascade using quantitative and qualitative approaches (including in-depth interviews)

3. Study design

To address these objectives, we will conduct an observational cohort study in 220 pregnant women who will be recruited at the first antenatal care (ANC) visit from the Gugulethu Midwife Obstetric Units in Cape Town. We will follow the enrolled women through 12-months post-delivery.

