The primary analysis will focus on measuring the distribution of women across the PrEP cascade including: initiation, retention and adherence. **PrEP initiation** will be based on a woman’s uptake of PrEP and allow for stoppage and re-initiation; **PrEP retention** will be defined as not missing >1 visit among those on PrEP (with separate analyses of PrEP stoppage). For **PrEP adherence** for women on PrEP we will measure both **perfect adherence** (i.e. level of objective adherence throughout pregnancy and breastfeeding periods) as well as “**prevention-effective**” adherence (i.e. adherence before and during times of sexual activity) in participants through objective and subjective measures to evaluate agreement between the two measures, and the level of under- or over-reporting. Primary adherence analyses will use objective measures (TDF-DP from DBS) taken on all those who enrolled and initiated PrEP; subsidiary analyses will consider (i) other adherence measures and (ii) multiple imputation for missing adherence data.

- **Use of PrEP will be measured** through alternate definitions of the main outcomes (e.g. adherence by self-report versus adherence by pharmacy refill), compared using measures of agreement and will be analyzed as independent models to contrast estimated associations.

- **Measurement of prevention-effective execution:** Execution refers to PrEP adherence during a time when at-risk sex happens. It is calculated by: number of doses reported, or recorded/number of expected doses based on HIV risk and PrEP initiation/discontinuation
- **Prevention-effective continuation:** Prevention-effective continuation describes the duration of PrEP use during periods of HIV risk and references the absolute time of use during pregnancy and breastfeeding periods. We will adapt the methodology from previous PrEP studies in SA including FEM-PrEP to create a semi-ordinal composite adherence score from blood specimens from DBS every 2-months.

Table 2: Study measures for PrEP-PP

Primary Outcomes	Measurement	Source	Frequency
PrEP initiation	# of women who initiate PrEP over time / total # of women in active cohort = proportion of women who initiate PrEP	Electronic provider log (REDCap)	Daily entry, weekly analysis

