PrEP retention	# of women on PrEP who return for study visits (do not miss more than 1 visit) / total # of women in active cohort who are prescribed PrEP= proportion of women on PrEP who are retained in PrEP study	Electronic provider log (REDCap)	Daily, analysis weekly
PrEP adherence-subjective	# of women taking PrEP, who self-report taking their medication daily (& pill count to confirm this) during periods of sexual risk over time / total woman-time on PrEP in active cohort = PrEP adherence rate (subjective)	Electronic provider log (REDCap)	Daily, analysis weekly
PrEP adherence-objective	# of women taking PrEP who have >80% levels at >40ng/mL TDF-DP (indicating dosing in past 24 hours) at 3 rd trimester, delivery, and 6 weeks postpartum (and during sexual risk periods during that time) / total woman-time on PrEP in active cohort = PrEP adherence rate (objective)	Lab analysis of TDF-DP measures	Quarterly
Secondary Outcomes			
Predictors of attrition at key steps in the PrEP cascade	Individual, pill/study and disease specific predictors of attrition	ACASI	ACASI: Every study visit
HIV outcomes	HIV testing data: HIV-uninfected, HIV-positive for mother and child (if mother seroconverts)	Electronic provider log (REDCap)	Every visit
Health outcomes and adverse events	Any side-effects, creatinine, any negative maternal or neonatal outcomes (for mother and infant)	Electronic provider log (REDCap)	During routine lab tests and visits

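### The primary cascade measures do not nest, so the planned summaries do not give the share of women who, at a given time, have started PrEP, are still attending and have adequate drug levels

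*Combined protocol and SAP*

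**What the plan says.** The closing paragraph of the background says the study will "determine the distribution of women across the PrEP cascade". Objective 1 in Section 2 repeats this, and Section 6 makes it the primary analysis: "The primary analysis will focus on measuring the distribution of women across the PrEP cascade including: initiation, retention and adherence". The design is an "observational cohort study in 220 pregnant women", followed to 12 months after delivery.

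The steps are then defined one at a time.

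- **Initiation.** Objective 1 counts women "who initiate PrEP out of all women offered PrEP". Table 2 takes the number "of women who initiate PrEP over time / total # of women in active cohort = proportion of women who initiate PrEP". Section 6 allows for stopping and restarting.
- **Retention.** No more than one missed visit among women on PrEP. The Table 2 denominator is "total # of women in active cohort who are prescribed PrEP". No time of assessment is given.
- **Objective adherence.** Section 6 uses TDF-DP from DBS "taken on all those who enrolled and initiated PrEP" and describes adherence across pregnancy and breastfeeding. Table 2 divides women above a level by total woman-time on PrEP. Its sampling points run from the third trimester to "delivery, and 6 weeks postpartum (and during sexual risk periods during that time").

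The modelling text in Section 6 describes each outcome by its own cumulative incidences at fixed intervals, with initiation by delivery as the only example. It adds time to loss among women who initiated. The only agreement analysis compares adherence measures with one another.

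**The concern.** A cascade is read from left to right: of the women enrolled, how many started, how many of those are still in care, and how many of those have protective drug levels. That reading needs each step to be a subset of the one before it, on a common time point. Here adherence is not conditional on retention in either definition, its Table 2 denominator is person-time rather than women, and the time windows of the three steps are not aligned.

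What is at stake is the last bar of the cascade. That is the figure a policymaker would take from a pilot meant to inform PrEP integration into antenatal and postnatal care. If it is not defined in advance, readers will multiply the separate percentages, or the analysts will choose time points and denominators after seeing the data.

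**Working it through.** The plan gives no expected proportions, precision or power for the cascade, so there is no figure to reproduce. The check is whether the planned summaries determine the joint share. All step proportions below are assumptions; only the 220 comes from the protocol.

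**1. The definitions side by side**

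| Step | Counted | Divided by | Time |
|---|---|---|---|
| Initiation (Table 2) | women who initiate | active cohort | over time, no fixed point |
| Retention (Table 2) | women on PrEP missing at most one visit | active cohort prescribed PrEP | not stated |
| Adherence (Table 2) | women above the TDF-DP level | woman-time on PrEP | third trimester, delivery, 6 weeks postpartum |
| Adherence (Section 6 text) | women by objective level | all who enrolled and initiated | pregnancy and breastfeeding |

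Initiation and retention could be chained if prescribed means initiated, the denominator is fixed and both are read at the same time. Adherence cannot be chained to retention under either definition.

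**2. Joint share from separate proportions**

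Let I be the number of initiators, and r and a the proportions of initiators retained and adherent. The number both retained and adherent is r·a·I under independence. It lies between r·a·I and min(r, a)·I under positive dependence. The mathematical minimum is max(0, r + a − 1)·I.

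With 80% initiation, r = 0.70 and a = 0.60:

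- I = 0.80 × 220 = 176; retained 0.70 × 176 = 123; adherent 0.60 × 176 = 106.
- Independence: 0.42 × 176 = 73.9, about 74 women (34% of 220).
- Upper limit: 0.60 × 176 = 105.6, about 106 women (48%).
- Mathematical minimum: 0.30 × 176 = 52.8, about 53 women (24%).

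With 60% initiation, r = 0.60 and a = 0.50: I = 132. Independence gives 0.30 × 132 = 39.6, about 40 women (18%). The upper limit is 0.50 × 132 = 66 women (30%). The mathematical minimum is 0.10 × 132 = 13.2, about 13 women (6%).

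For scale, the 95% half-width for a share of 34% in 220 women is 1.96 × √(0.336 × 0.664 / 220) = 0.062, about 6 percentage points. The gap between 34% and 48% is about 14 points.

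**3. The Table 2 adherence figure is not a share of women**

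Take the same 106 adherent women among 176 initiators (60%) and divide by woman-years, 176 × (mean months on PrEP) / 12:

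| Mean months on PrEP | Woman-years | Adherent women per woman-year |
|---|---|---|
| 3 | 44 | 2.41 |
| 6 | 88 | 1.20 |
| 12 | 176 | 0.60 |
| 18 | 264 | 0.40 |

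The figure moves with duration of use although the number of adherent women does not change.

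**4. The active cohort**

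The term is not defined. Suppose it excludes censored women, and that those excluded are initiators who were not retained. Retention of 123/176 = 70% becomes 123/156 = 79% after removing 20 women, and 123/136 = 90% after removing 40. Initiation times retention then rises from 123/220 = 56% to 123/200 = 62% and 123/180 = 68%.

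**The case against.** The best answer to the concern is that objective 1 spells out what it means by a distribution: separate proportions who initiate, who are retained and who adhere among initiators. The plan can report each of these, and narrowing denominators are normal in a cascade. That stands. A reader might infer that objective 1 cannot be met at all; its own list of sub-objectives does not support that.

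Three further inferences are tempting and also go too far.

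- **That adherence is measured only to six weeks postpartum.** One row of Table 2 reads that way. But the text of Section 6 covers the breastfeeding period and a composite score from two-monthly DBS, and Table 1 schedules DBS to month 18. The fault is that the two definitions disagree.
- **That retention covers the whole of follow-up.** No window is stated.
- **That the joint share is uncertain over the full 24% to 48%.** The lower end needs retained women to be less often adherent than the others. That is unlikely, because a DBS sample requires an attended visit.

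The fixed-interval cumulative incidences could put the outcomes on a common time basis. They remain separate for each outcome, so the overlap is still not given. Time to loss among initiators links initiation to retention, not to adherence. Nor is anything lost for good: visit, dispensing and DBS data are held per participant. The pilot's lack of power for differences between steps is a fair caveat on precision, but it does not supply a definition of the main result.

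**Conclusion.** The concern holds as a gap in the definition of the primary result. Followed literally, Table 2 gives steps that do not nest and an adherence figure that is not a proportion of women. The planned summaries leave open the share who have initiated, are attending and have TDF-DP at or above the cut-off at a given time.

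On the first set of assumed proportions the plausible range is about 74 to 106 women, or 34% to 48% of 220, which is more than twice the sampling half-width. On the second set it is 40 to 66 women, or 18% to 30%. These sizes rest on the assumed step proportions and on non-negative dependence between retention and adherence. The inflation shown for the active cohort rests on reading that term as excluding censored women. The absence of a joint classification rests on the text alone. The gap should be closed before analysis, and it needs no new data.

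**What to change.** Add one prespecified table to the primary cascade result, at named scheduled visits with DBS: the first postpartum visit, and about 6 and 12 months postpartum (months 7, 13 and 18 in Table 1). Use all enrolled women as a fixed denominator, say how that differs from the women offered PrEP in objective 1, and give 95% confidence intervals. Place each woman in exactly one state:

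1. never initiated;
2. initiated, then stopped PrEP, still attending;
3. initiated and lost to follow-up;
4. censored for seroconversion, moving away or transfer, shown separately;
5. on PrEP and attending, no DBS result, shown separately, with the multiple imputation already named in Section 6 as a sensitivity analysis;
6. on PrEP and attending, TDF-DP below the cut-off;
7. on PrEP and attending, TDF-DP at or above the cut-off.

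State an order of precedence, so that a woman who meets two descriptions (for example, never initiated and later moved away) is counted once. Report stopping alongside reported sexual risk, so that stopping consistent with the plan's prevention-effective concept is not read as failure.

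Reconcile the adherence window and denominator between the Section 6 text and Table 2. Also reconcile the TDF-DP cut-off, which is at least 40 ng/dl in the laboratory section and above 40 ng/mL in Table 2. Define the active cohort, and keep the Table 2 rows as supporting measures.

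The cost is one cross-classification of data already collected. The final step will look less favourable than the separate percentages.

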Setting. The study will take place in two urban townships in Cape Town (Gugulethu MOU) with high HIV incidence that span the different socioeconomic, cultural, and ethnic groups in South Africa. We selected this community because of the high HIV prevalence there in pregnant and breastfeeding women, and because of the high number of mothers visiting every month for ANC and labour/delivery. Further, our team has several years' experience implementing research studies in those MOUs which will facilitate the integration of the study there. In 2017, Gugulethu saw over 3300 new ANC consultations per month, and 72% (n=2300) are HIV-negative. Considering our experience and patient flow, we are confident that at least 60 women/month per facility can be enrolled. Further, Drs. [name], [name] and colleagues have conducted research in the Gugulethu community for more than a decade and have substantial experience partnering with local health services. Building on this platform, we will use existing infrastructure in each clinic, including capacitating existing clinical providers, pharmacists and counselors, to provide PrEP care to pregnant and breastfeeding mothers. We will hire study staff to assist in the coordination, data management, and overall quality assurance of the counseling, drug provision and participation follow-up.

4. Study population

Study counselors will enroll consecutive eligible, consenting pregnant adolescent girls (≥ 16 years) and women in ANC (N=220 pregnant women) and follow them up for 12-months postpartum or until censorship for a mean of 18-months' follow-up.

Inclusion Criteria:

1. ≥ 16 years old
2. confirmed HIV-negative (using 2 rapid HIV test kits, confirmed with a 4th generation antigen HIV test),
3. lives within 20 kilometers of a clinic

4. confirmed to be pregnant
5. without psychiatric or medical contraindications to PrEP

Exclusion criteria:

Individuals not meeting the above criteria or meeting any of the following criteria will be excluded:

- Concurrent enrolment in another HIV-1 vaccine or prevention trial
- Medical hospitalization in the past year for any reason
- Receipt of TB treatment within the past 30 days
- History of renal disease
- Exhibiting psychotic symptoms (including hallucinations, suicidal or homicidal ideations, or violent behaviour)
- Currently or history of taking an anti-psychotic medication (such as for treatment of bipolar disorder, schizophrenia, or postpartum psychosis following a previous pregnancy)

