Step 11: Participants will receive counselling on the risks and benefits of PrEP. Following the counseling they will be asked: “Do you want to start taking PrEP today to prevent HIV? You will need to take it daily for it to be effective.” Her response will be recorded.

If yes:

1. The nurse will provide the participant with a 1-month supply of TDF-FTC and invite her to return in 1 month for her next study visit.
2. Nurses will provide contact information to the participant and ask her to call to report any side effects or adverse events while on PrEP, and nurse will track and report serious adverse events to study PIs, Pediatrician, and Obstetrician to decide on how to treat women and infants who have adverse events.

If she says she does not want to start PrEP, woman will be in the deferred PrEP arm:

1. The nurse will schedule her to return in 1 month for the follow-up visit

Step 12: Participants will receive study staff contact information, instructions to call with any questions, and will be scheduled for their next visit in 1 month for the next study visit

Step 13: Participants will receive study staff contact information, instructions to call with any questions, and will be scheduled for their next visit in 1-week to return when test results have returned from the laboratory

Step 14: The study counselor will provide the mother with an appointment card and invitation for her partner to return to receive couples’ HIV testing and counseling (if in a relationship). The session will end by encouraging the client to implement her/his risk-reduction plan (including PrEP if applicable and consistent condom use, couples testing) to prevent HIV acquisition.

Step 15: The participant will receive up to R250 per visit including reimbursement for the participant’s time, transportation and including their refreshments during the study. Further, we will combine the study visits with existing ANC or post-partum/well-baby visits to minimize the travel to the facilities outside of normal clinical checkups.

2. For follow up return visits:

Follow up visits will be monthly until birth (to coincide with ANC visits) then every two months after birth (to coincide with post-partum, well-baby visits).

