Step 1: In ANC: Healthcare providers provide counseling on HIV prevention and treatment at each ANC visit including HIV testing, as part of standard of care. In post-natal care and well-baby visits women may not receive regular HIV testing and messages and will receive this within step 2 (with study counselor). Following their ANC visit, enrolled women will be invited to attend the study site in each MOU to do the follow-up visit including the ACASI survey and prescription and adherence counseling (if on PrEP).

Step 2: ACASI survey at each visit in a private study room

Step 3: In the study room, the study counselors will provide PrEP-specific counseling including adherence counseling for those on PrEP (and management of side effects), or counseling about the risks and benefits of PrEP for women not yet on PrEP. Women not on PrEP will be asked if they are interested in starting PrEP at this visit.

Step 4: STI testing: At 3rd trimester visit and first postpartum visit, participants self-collect a vaginal swab for STI testing (chlamydia, gonorrhea and trichomonas vaginalis using Cepheid® point of care testing). Participants will be treated if diagnosed with a STI according to National Guidelines. They will receive a partner notification letter to bring their partner in for treatment as well.

Step 5 (for women on PrEP): At each visit the study counselor will ask, and record responses, all participants on PrEP about any side effects associated with TDF/FTC, including diarrhea, nausea, fatigue, headache and rash (which are seen in about 10% of participants during the initiation of therapy). We will encourage participants to contact the study nurse if they experience side effects between visits.

For participants on PrEP, the study nurse performs a blood draw for creatinine clearance and a finger prick for DBS testing for adherence measures and (if applicable for this visit). See Table 1 for study calendar.

Step 6: PrEP provision (for 1 or 2 months) and appointment reminder

Follow-up & retention: Tracing information will be taken at the enrolment visit and updated at each study visit. Retention activities will focus on scheduled measurement visits. Following our established approach in this setting, we will provide reminder calls to participants before their measurement visits, and initiate tracing, including home visits, for women who do not attend the measurement visit within one week of the scheduled visit.

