 - If a woman seroconverts while on PrEP, there may be a risk of ART resistance, though research has demonstrated that the risk of ART resistance is very low [12, 13]. In the case of seroconversion, Drs [name] and [name] will follow seroconverters with the study team to evaluate if the patient achieves viral suppression within 6 months of ART start, and if not, she will be referred for specialist attention for testing for ART resistance and clinical follow-up.

Adverse events:

- **Maternal adverse events:** We will collect data on maternal adverse events by asking mothers about intercurrent medical events, which will be reviewed by an obstetrician, including any hospitalizations or illnesses. We will also track and report changes in creatinine or other toxicities in women on PrEP.
- **Infant adverse events:** We will collect data on infant adverse events by asking mothers about infant health or intercurrent medical events, which will be reviewed by a pediatrician.
 - Adverse birth outcomes will include infants that were small for gestational age, pre-term births, miscarriage and stillbirths.

Table 1: PrEP-PP cohort measures by participant study month

Participant study month	Pregnancy						Post-partum											
	1	2	3	4	5	6	7	8	9	10	11	12	13	14	15	16	17	18
Study enrollment and consent of consecutive sample of HIV-negative pregnant women (N=220)	X																	
PrEP group, individual (or couples counseling where applicable) and information, education, counseling materials on PrEP in pregnancy and breastfeeding in local languages (at each visit)	X	X	X	X	X	X	X		X		X		X		X			X
Routine ANC and postnatal care, well-baby visit follow-up (as available in standard of care), including rapid HIV testing, pregnancy, and birth outcomes	X	X	X	X	X	X	X		X		X		X		X			X
ACASI survey to collect: behavioral acceptability, knowledge, and substance use data	X	X	X	X	X	X	X		X		X		X		X			X
Screening at enrolment for Hepatitis B surface antigen. If HBsAg+ = excluded from study	X																	
Laboratory testing for STIs (chlamydia and gonorrhoea) & treatment if positive	X				X		X											
For women on PrEP:																		
Laboratory tests of creatinine (if eGFR<60ml/min cannot continue on PrEP, refer to return in 1 month for re-test)	X			X			X								X			X
PrEP pharmacy refills and adherence supportive counseling monthly (for first 3 months on PrEP) then every 2 months for following months	X	X	X		X		X		X		X		X		X			X

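### The primary retention rule allows one missed visit however many are due, so at equal per-visit attendance women with more visits due are less likely to count as retained

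*Combined protocol and SAP*

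**What the plan says.** Section 6 (statistical analysis considerations) states that retention "will be defined as not missing >1 visit among those on PrEP", with PrEP stoppage analysed separately. Table 2 lists retention as a primary outcome, reviewed weekly, and gives the ratio as women who "do not miss more than 1 visit) / total # of women in active cohort who are prescribed PrEP". Neither place states a time point, a minimum number of visits due, or whether misses are cumulative or consecutive.

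The rest of the protocol makes the number of visits due vary between women:

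- **Entry.** Women are "recruited at the first antenatal care (ANC) visit" (section 3), and section 4 sets no gestational-age criterion.
- **PrEP start.** PrEP is offered at enrolment. After that, "Women not on PrEP will be asked if they are interested in starting PrEP at this visit" (section 5, follow-up visits, step 3). The initiation outcome will also "allow for stoppage and re-initiation" (section 6).
- **Visit spacing.** "Follow up visits will be monthly until birth (to coincide with ANC visits) then every two months after birth" (section 5).
- **End of follow-up.** The study will "follow them up for 12-months postpartum or until censorship" (section 4), so the end is tied to delivery and not to PrEP start.

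Section 6 also promises, for every outcome, cumulative incidence at set intervals and product-limit graphs. For retention it adds a time-to-event analysis of loss among initiators.

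**The concern.** A fixed allowance of one miss is a strict test for a woman with many visits due and a lenient one for a woman with few. A month-1 starter who misses two visits but attends at month 18 is not retained. A month-15 starter who never comes back has missed only one visit and is retained.

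The single proportion in Table 2 therefore mixes attendance with the timing of PrEP start and of enrolment in pregnancy. It would be hard to interpret alone or to set beside another programme's figure. The weekly tabulation has the same defect: at any look, a woman with no visit or one visit due so far cannot yet have failed.

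**Working it through.** The documents state no expected retention or attendance rate, so there is no figure of the plan's own to reproduce.

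**Visits due.** The Table 1 row "ACASI survey to collect: behavioral acceptability, knowledge, and substance use data" marks visits at months 1, 2, 3, 4, 5, 6, 7, 9, 11, 13, 15 and 18 (column positions as read from the extracted table). Counting visits after PrEP start gives n.

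| PrEP start | Visits due, n | Share needed, (n − 1)/n |
|---|---|---|
| Month 1 | 11 | 10/11 = 91% |
| Month 7 | 5 | 4/5 = 80% |
| Month 11 | 3 | 2/3 = 67% |
| Month 15 | 1 | 0/1: cannot fail |

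This table needs no assumption about attendance.

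**Size, cumulative reading.** Assume that every woman attends each visit with the same probability p, independently. Then P(retained) = p^n + n(1 − p)p^(n−1). At p = 0.90:

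- n = 11: 0.3138 + 11 × 0.1 × 0.3487 = 0.697
- n = 5: 0.5905 + 5 × 0.1 × 0.6561 = 0.919

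The value of p is an assumption, so a range is shown.

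| p | Month 1 (n = 11) | Month 7 (n = 5) | Gap, points |
|---|---|---|---|
| 0.95 | 89.8% | 97.7% | 7.9 |
| 0.90 | 69.7% | 91.9% | 22.2 |
| 0.85 | 49.2% | 83.5% | 34.3 |
| 0.80 | 32.2% | 73.7% | 41.5 |

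**Gestation at entry.** Two women start PrEP at enrolment, one with 5 antenatal follow-up visits left and one with none. With 6 postpartum visits each, they have 11 and 6 due: 69.7% against 88.6% at p = 0.90.

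**Clustered misses.** With a beta-binomial model at p = 0.90, month 1 against month 7 is 71.3% against 88.8% (within-woman correlation 0.1), 73.7% against 87.4% (0.2) and 78.5% against 86.8% (0.4).

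**Consecutive reading.** If only two misses in a row count as failure, P(retained) = Σ_k C(n − k + 1, k)(1 − p)^k p^(n−k). This gives 91.1% against 96.3% at p = 0.90 (5 points) and 70.2% against 86.5% at p = 0.80 (16 points).

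**Refill schedule.** Table 1 also has monthly refills for the first 3 months on PrEP, which would give a month-7 starter an extra visit at month 8. Counting refill visits only gives 9 against 6 due, and 77.5% against 88.6% at p = 0.90. Counting all study visits gives 11 against 6, and 69.7% against 88.6%.

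**Two simple repairs, at p = 0.90.** Keeping the missed-visit rule but limiting it to 6 months from PrEP start leaves 6 visits against 3: 88.6% against 97.2%, still 8.6 points apart because visit spacing changes at birth. Requiring at least 80% of due visits gives 91.0% (n = 11), 88.6% (n = 6), 91.9% (n = 5) and 72.9% (n = 3), which is erratic when few visits are due.

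**The case against.** The strongest reply is that section 6 already handles unequal follow-up: interval-based cumulative incidence, product-limit graphs, and time to loss among initiators. That stands in part. The only interval given as an example concerns initiation by delivery. For retention, no interval, time origin or event date is named, the time-to-event analysis is additional and aimed at associated factors, and the Table 2 proportion is unchanged. If the event is the second missed visit, time before birth still carries twice the visit rate of time after it.

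A second reply is that consecutive misses may be meant. Section 6 equates non-retention with loss, and section 4 describes loss as more than 8 weeks without a visit in a woman who cannot be traced. That reading is plausible. It shrinks the gap without removing it, and the text does not adopt it.

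A third is that this is a pilot not powered for comparisons. True, but the problem is what the proportion measures, not its precision, and section 6 offers the pilot as a source of cascade estimates.

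A reader might also infer more than the documents support:

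- **That the study's retention figure will be wrong by some 22 points.** That number depends on assumed 90% attendance, independent cumulative misses, and one contrast of start times. PrEP is offered on the enrolment day, and nothing shows how many women will start late.
- **That the planned comparisons are confounded.** The main exposures listed in section 6 do not include time of PrEP start, gestation or pregnancy period. Confounding through a correlated predictor is possible but not shown.
- **That the denominator drops women once they are lost.** The term active cohort is not defined. This is a natural inference, not a stated rule, and if true it could offset part of the gap.
- **That women with the same number of misses are treated differently.** They are classified alike. The point concerns equal attendance probability or proportion.

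**Conclusion.** The point holds. As written, the primary retention proportion depends on the number of visits due, and so on PrEP start and gestation at entry. The direction is the same in every scenario computed, and the unequal attendance shares follow from the calendar alone.

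The size is uncertain. For month-1 against month-7 starters it runs from about 8 points at 95% attendance to about 42 at 80%, with independent cumulative misses. It is about 8 points at 90% attendance with strong clustering (correlation 0.4), and about 5 at 90% if only consecutive misses count. The effect on the overall proportion cannot be computed, because the distribution of start times is unknown. Since this is a primary outcome, the definition should be settled before the data are analysed.

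**What to change.** Make the primary retention measure a proportion at fixed times since PrEP start, for example 3, 6 and 12 months:

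- **Numerator:** women who attended a study visit within a stated window around that time. Every start month needs a due visit in its window: 3 months after a month-7 start is month 10, between the visits at months 9 and 11. Naming the due visit nearest the landmark would avoid giving some women more chances than others.
- **Denominator:** all women who initiated PrEP and whose planned follow-up reaches that time, with women lost to follow-up counted as not retained. This replaces the undefined active cohort.
- **Support:** a product-limit curve of time from PrEP start to loss, with the event and its date defined.

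Report delivery and postpartum landmarks only by time of PrEP start, because they fall at different times since starting. Keep stoppage as the separate analysis already planned. Keep the missed-visit count as a descriptive measure, stating whether misses are cumulative or consecutive.

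The cost is SAP wording; the data are already collected. The retention figure may be lower, and late starters do not contribute to later landmarks: with follow-up ending at month 18, a month-7 starter cannot reach 12 months (7 + 12 = 19).
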